Project Title

Synergizing home health rehabilitation therapy to optimize patients' activities of daily living

Investigators

PI: [name], OTR/L, FGSA, UF Department of Occupational Therapy

CO-I: [name], PT, UF Department of Physical Therapy

CO-I: [name], UF Department of Biostatistics

Conflict of interest

All the investigators declare no conflict of interest.

Clinical Trial Registration #: NCT05411393

UF IRB202102816

Supported by the National Institute on Aging (R21 AG076972)

Date: 1/30/2024

Abstract

Regaining the ability to take care of oneself after an illness or medical episode is critical for older adults to maintain independent living at home in the community. Each year, 3 to 4.5 million older adults receive home health care services that provide skilled rehabilitation therapy in their home. These patients experience reduced capacity to perform activities of daily living (ADL) independently, which is a significant risk factor for long-term care placement. Recent data has shown that nearly 40% of home health patients do not improve in ADL at discharge. There is currently a lack of evidence-based rehabilitation programs in home health. Increasing activity-based intervention in home health care rehabilitation could be the key to improve patients' ADL independence. The objective of this study is to pilot test an ADL-enhanced program as an adjuvant therapy to usual home health rehabilitation to improve patients' ADL outcome. The ADL-enhanced program facilitates patients' participation in ADL first by lowering the task demand using a compensatory approach. As the patient increases physical capacity, the ADL-enhanced program shifts to a restorative approach, which increases the task demand to help the patient channel the improved physical capacity to better activity performance. Our specific aims were to: 1) estimate the preliminary effect of the ADL-enhanced program on improving ADL; 2) estimate the preliminary effect of the ADL-enhanced program on improving physical functioning of the upper extremity and the lower extremity; and 3) assess the program completion rate, satisfaction rate, and adverse event rate (e.g., falls and hospital admissions).

Study Objectives

Primary Objective.

The primary objective is to estimate the preliminary effect of the activities of daily living (ADL)-enhanced program on improving ADL at treatment completion, one month, and 3 months after the completion.

Hypothesis: Patients who receive the ADL-enhanced program plus usual rehabilitation therapy will show greater improvements in the Motor Skills scores of the Assessment of Motor and Process Skills (the primary outcome), Self-care items in the Outcome and Assessment Information Set (clinical outcome), and Activity Measure for Post-Acute Care Home Health Short Form (patient-reported outcome) at treatment completion and less decline at 1-month and 3-month follow-up than usual rehabilitation therapy.

Secondary Objectives.

Secondary objective 1: To estimate the preliminary effect of the ADL-enhanced program on improving physical functioning at treatment completion and one month after the completion.

Hypothesis 1: Patients who receive the ADL-enhanced program plus usual rehabilitation therapy will show greater improvements in the Box and Block Test (upper extremity physical function), Jebsen Hand Function Test (upper extremity physical function), Timed-Up-and-Go Test (lower extremity physical function), and Short Physical Performance Battery (lower extremity physical function) at treatment completion and less decline at one-month follow-up than usual rehabilitation therapy.

Secondary objective 2: To assess the completion, satisfaction, and adverse event rates of the ADL-enhanced program.

Hypothesis 2a: We hypothesize that the program completion and satisfaction rates will be greater than 75%.

Hypothesis 2b: Fewer patients who receive the ADL-enhanced program will have hospitalizations, emergency room visits, and falls than patients who receive usual rehabilitation therapy at 1-month and 3-month follow-up.

Background and Rationale

Preserving older adults' ability to perform activities of daily living (ADL) is critical to reducing risks of hospital admission and readmission, long-term care placement, and mortality, especially after an acute hospital stay or illness when they experience an ADL decline. Each year, 3 to 4.5 million U.S. patients receive home health care (HHC), which provides in-home skilled rehabilitation services to homebound patients. These patients are often of advanced age and with multiple chronic conditions, poor health, and worsened functional status. A recent study indicates that 6% of HHC patients show no improvement in ADL status, and 36% show a decline in ADL status from admission to discharge. Numerous community-based intervention trials have provided strong evidence of two intervention approaches to reduce ADL disability in frail older adults: (1) **the compensatory approach** reduces the demands of the patient's intrinsic capacity to perform activities through home or task modifications (e.g., adding a shower bench or taking a sponge bath by the sink); (2) **the restorative approach** increases a patient's intrinsic capacity to perform activities through exercise (e.g., resistance exercise to improve leg strength). However, neither approach has been tested in the HHC setting.

Our proposed ADL-enhanced intervention is innovative because it delivers the compensatory approach first in HHC rehabilitation services to help the patient engage in ADL tasks immediately, followed by the restorative approach to increase the patient's intrinsic capacity needed to perform activities. Additionally, the restorative approach incorporates principles of activity grading and motor learning to help older adults translate muscle strength from resistance exercise into greater ADL performance.

In this proposed pilot randomized controlled trial, we will test the preliminary effects of the innovative ADL-enhanced program, which combines the compensatory approach and restorative approach in six OT visits to boost usual rehabilitation services on the ADL outcome in enrolled HHC patients.

Study Design

Study design overview. This is a single-blinded, pilot randomized controlled trial of 48 Medicare patients referred to HHC for skilled rehabilitation services. Twenty-four patients will be randomly assigned to the treatment-as-usual arm and receive usual rehabilitation services. The other 24 patients in the experimental arm will receive the ADL-enhanced program in six OT visits as well as usual rehabilitation services.

Selection and Enrollment of Participants

Participants will be recruited from partnered home health agencies

Inclusion criteria. Patients are eligible to the study if they are:

- (1) \geq 65 years of age,
- (2) Medicare beneficiaries,
- (3) referred for skilled rehabilitation services; and
- (4) diagnosed with three or more comorbidities.

Exclusion criteria. Patients are ineligible if they have contraindications for moderate-intensity exercise, which include:

- acute fractures with surgical or weight-bearing restrictions,
- elective joint replacement surgery,
- lower extremity amputation,
- active treatment for cancer diagnosis,
- on-going dialysis treatment,
- acute cardiac surgery,
- acute stroke or a major neurologic disorder limiting motor movements,
- terminal stage of congestive heart failure,
- a referral to hospice care, or
- severe cognitive deficits limiting verbal communication.

Enrollment Procedures.

Screening procedure. The home health care team will obtain verbal permission from new patients to allow the research coordinator to contact and screen the new patients via phone. The coordinator will record the screening results (fail or pass) on a screening log. The coordinator will call the eligible patient, verify the eligibility, and introduce the study.

Consent procedure. The coordinator will then conduct a recruitment home visit to the eligible patient and obtain consent at the end of the visit. If the patient does not provide consent during the recurrent home visit but decides to participate in the study afterwards, a study outcome assessor will obtain consent at the beginning of the baseline assessment visit. Reasons of rejection will be recorded.

Patients who are eligible and agree to participate will be referred to the study outcome assessor, who will schedule the patient within 48 hours to obtain the consent, if not yet obtained by the research coordinator, and complete the baseline assessments (ADL and physical functioning assessments) at the participant's home. The assessor will be blinded to group assignments.

Randomization procedure. [name] (Co-I) will generate a randomization list using a computer software and seal the list in opaque envelopes. The on-site research coordinator will open one envelope after a patient has completed the baseline assessments. If the patient is assigned to the ADL-enhanced group, the coordinator will notify the study OT to start intervention.

Study Intervention.

Description of ADL-enhanced intervention. The experimental arm will receive the enhanced-ADL program in 6 home visits from a study OT in addition to usual rehabilitation therapy. The 6 study visits will be delivered over

a 6-week period. The study OT visits will occur separately from usual therapy visits. If the patient cancels a study OT visit, the visit will be rescheduled. The patient will have a 21-day window to resume the intervention. The study OT will apply the compensatory approach in the first 2 visits and the restorative approach in the other 4 visits. Both approaches respect and incorporate the patient's activity preferences in the patient-centered treatment plan. The study OT and the patient collaborate to identify and address ADL tasks that are important and meaningful for the patient's independence.

Compensatory approach procedures. The study OT will conduct a semi-structured interview in the 1st visit to understand the patient's daily routine and to identify two or three ADL tasks that are meaningful but difficult for the patient because of reduced intrinsic capacity. The study OT and the patient collaboratively decide which energy conservation techniques to apply. The patient practices applying these techniques to the selected ADL tasks. The patient is instructed to carry out these ADL tasks with practiced energy conservation techniques until the next visit.

Restorative approach procedures. The study OT will deliver the restorative approach starting at the 3rd visit. The selected self-care tasks include any in-home activities that the patient does to take care of self and others, which are not limited to basic ADL. In the beginning of each visit, the study OT and the patient together identify 2 or 3 activities where the patient has experienced limitations or difficulties. The study OT will apply one or two activity grading principles to each selected activity. The intervention intensity will be kept at the moderate level (somewhat hard) using the Omni Scale, which is a rated perceived exertion scale. For example, if a patient experiences difficulty to returning pantry items to overhead shelves, the study OT can let the patient wear a weighted wrist cuff while sorting pantry items (increase the load), restore items to an overhead versus shoulder-high shelf (increase the movement distance), restore items into different locations on the shelves (change of movement direction), speed up while storing items (increase the movement speed), store 10 pantry items versus store five items at a time (increase the endurance), or carry groceries with a shopping bag and store pantry items from the groceries to the overhead shelves (increase the activity complexity by combining two tasks, carrying groceries and sorting the pantry items after shopping). Patients will practice each selected task for 15 to 20 minutes with a rest break if needed.

Allowed interventions. All participants will receive the care plan approved by their home health agency. The care plan should include regular home health rehabilitation therapy.

Adherence Assessment. The adherence for the ADL-enhance intervention will be evaluated by the number of sessions that the patient is able to complete within the study period (60 days).

Study Procedures.

[figure not shown]
6.1. Schedule of Evaluations.

	Baseline	Post-intervention (Post intervention \pm 7 Business days) ⁺	One-month follow-up (Day 30 post intervention \pm 7 Business days)	3-month follow-up (Day 90 post intervention \pm 7 Business days)
Assessment of Motor and Process Skills	x	x	x	
Activity Measure for Post-Acute Care Home Health Short Form	x	x	x	x
OASIS self-care items from chart review	x	x		
Box and Block Test	x	x	x	
Jebesen Hand Function Test	x	x	x	
Timed-Up-and-Go Test	x	x	x	
Short Physical Performance Battery	x	x	x	
PEG three-item scale	x			
Patient Health Questionnaire-9	x			
Saint Louis University Mental Status Exam	x			

Patient demographic background and medical info from self-report as well as chart review	x			
Patient satisfaction survey		x		
Adverse events (hospitalization, falls, emergency room visits)		x	x	x

+: The end of ADL-enhanced program, the last home visit of usual care, or 6 weeks from the baseline assessment, which occurs last.

Study visit schedule.

Description of Evaluations.

Screening evaluation.

The screening will occur over the phone within three business days after a home health care provider has mentioned the study opportunity to the patient and received verbal permission from the patient for the research coordinator to contact him/her. The research coordinator will follow a phone script approved by the UF IRB for this phone screening. The coordinator will obtain a verbal permission prior to proceeding with screening questions from the potential research participant after a brief introduction of the study. These screening questions are:

1. Are you aged 65 years or above?
2. How many medical conditions, including chronic conditions, that you currently have? Examples of the conditions include but not limit to diabetes, heart disease, high blood pressure, joint disease or arthritis, and lung disease.
3. Do you have any of the following conditions?
 - an elective joint replacement surgery in the last month
 - orthopedic or heart surgery in the last month
 - lower extremity amputation
 - currently receiving treatment for cancer
 - an ongoing dialysis treatment
 - a neurologic condition, such as stroke or Parkinson's disease, that significantly limits your movements
 - congestive heart failure that is at the terminal stage

In addition to these questions, the interviewer will administer the "Six-item cognitive screener" to determine the potential participant's cognitive ability. If a participant scores a 4, 5, or 6 on the screener, they will be eligible for the study.

Enrollment, baseline, and randomization.

Enrollment. A patient is considered enrolled in this study when he or she meets the eligibility criteria and signs the informed consent form.

Consenting process. If the patient passed the screening, the research coordinator will then conduct a recruitment home visit to the eligible patient within five business days. During the visit, the coordinator will provide the patient with a detailed description of the research study and go over the informed consent process. If the patient does not provide consent during the recurrent home visit but decides to participate in the study afterwards, a study outcome assessor will obtain consent at the beginning of the baseline assessment visit. If the patient decided not to enroll, the reason(s) of rejection will be recorded.

Baseline assessment. The enrolled patient will be then referred to the study outcome assessor, who will schedule the patient to obtain the consent, if not yet obtained by the research coordinator, and complete the baseline assessments at the participant's home. The baseline assessment should occur within seven business days of the recruitment visit. The assessor will be blinded to patient group assignments. The blinded outcome assessor will conduct the following assessments during the baseline evaluation visit. These assessments are listed in suggested order. The outcome evaluator will alternate between self-reported assessments and performance-based assessments as well as upper extremity performance tests and lower extremity performance tests to reduce the testing burden for patients. Additionally, short breaks (one to five minutes) between assessments will be provided to patients as needed.

1. Demographic information of age, gender, race/ethnicity, chronic conditions, and number of medications
2. Assessment of Motor and Process Skills
3. Activity Measure of Post-Acute Care Home Health Short Form
4. Jebsen Hand Function Test
5. Box and Block Test
6. PEG three-item scale
7. Patient Health Questionnaire-9
8. Timed-Up-and Go
9. Short Physical Performance Battery
10. Saint Louis University Mental Status Exam.

The research coordinator will extract the patient's OASIS self-care item scores (scores at the start of care and discharge) from medical chart when the patient has been discharged from home health care or 60 days after admission.

Randomization. Randomization will occur after the baseline assessment. [name] (Co-I) will generate a randomization list using a computer software and seal the list in opaque envelopes. The on-site research coordinator will open one envelope after a patient has completed the baseline assessments. If the patient is assigned to the ADL-enhanced group, the coordinator will notify the study OT to start intervention.

Post-intervention evaluation.

The satisfaction survey will be given to the patient in the experimental group after the last visit of ADL-enhanced intervention by the research coordinator over the phone.

For the group that will receive the ADL-enhanced program, the post-intervention evaluation conducted by the blinded outcome assessor will occur within seven business days after the completion of the last visit of usual home health rehabilitation therapy or ADL-enhanced intervention, whichever occurs last. For the control group, the post-intervention evaluation conducted by the blinded outcome assessor will occur either 6 weeks after the baseline assessment or after the last usual home health visit, whichever occurs last. Patients will be instructed not to discuss their therapy content with the blinded outcome assessor and vice versa. The following assessments will be administered during the post-intervention evaluation visit.

1. Assessment of Motor and Process Skills
2. Activity Measure of Post-Acute Care Home Health Short Form
3. Jebsen Hand Function Test
4. Box and Block Test
5. Timed-Up-and Go
6. Short Physical Performance Battery
7. Adverse events questionnaire

The research coordinator will extract the patient's OASIS self-care item scores (scores at the start of care and discharge) from medical chart when the patient has been discharged from home health care or 60 days after admission.

One-month follow-up evaluation.

The one-month follow-up evaluation conducted by the blinded outcome assessor will occur within seven business days one month after the completion of the last visit of usual home health rehabilitation therapy or ADL-enhanced intervention (Day 30 post intervention), whichever occurs the last. Patients will be instructed not to discuss their therapy content with the blinded outcome assessor and vice versa. The following assessments will be administered during the one-month follow-up evaluation visit.

1. Assessment of Motor and Process Skills
2. Activity Measure of Post-Acute Care Home Health Short Form
3. Jebsen Hand Function Test
4. Box and Block Test
5. Timed-Up-and Go
6. Short Physical Performance Battery
7. Adverse events questionnaire

Final evaluation or three-month follow-up evaluation.

The final evaluation will occur over the phone by the research assistant or coordinator within seven days three months after the completion of the last visit of usual home health rehabilitation therapy or ADL-enhanced intervention (Day 90 post intervention). The following assessments will be administered during the final evaluation.

1. Activity Measure of Post-Acute Care Home Health Short Form
2. Adverse events questionnaire

Data analysis plan.

Preliminary analysis. We will compare participant demographics and covariates (e.g., pain levels) between the two groups. Variables with statistically significant differences will be included in the subsequent statistical models as covariates. We will graph spaghetti plots for repeated measurements and examine for outliers.

Data analysis. Since ADL and physical functioning outcomes will be collected over three time points (baseline, post-treatment, one-month follow-up), the mixed-effects linear regression modeling will be conducted to fit the data, in which a random-effects term is included to accommodate within-subject data correlation and a quadratic growth curve is included to describe the temporal trend of the response.

For **Aim 1**, which will estimate the preliminary effect of the ADL-enhanced program on improving ADL, three separate mixed-effects regression analyses will be conducted for the Motor Skills scores of the Assessment of Motor and Process Skills (the primary outcome), the Activity Measure of Post-Acute Care Home Health Short Form, and the OASIS self-care items, in each of which sex, race, age, and other covariates will be included in the model.

For **Aim 2**, which will estimate the preliminary effect of the ADL-enhanced program on physical functioning of the upper extremity and lower extremity, four similar separate analyses will be conducted for the Box and Block Test, Jebsen Hand Function Test, Timed-Up-and Go, and Short Physical Performance Battery.

For **Aim 3**, the program completion rate and satisfaction rate will be compared to the benchmark, 75%. Fisher's Exact Test will be performed to compare the proportion of patients who experience adverse events of hospitalization, emergency room visits, or falls (adverse event rate) between the two groups.

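### The primary hypothesis claims effects at completion, 1 month and 3 months on three ADL measures, but 3 of the 9 comparisons have no data and the analysis plan gives no 3-month AM-PAC contrast

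*Combined protocol and SAP*

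**What the plan says.** The Primary Objective is to estimate the effect on "improving ADL at treatment completion, one month, and 3 months after the completion". Its hypothesis names AMPS Motor Skills (primary outcome), OASIS self-care items and AM-PAC in one sentence. It predicts greater improvement "at treatment completion and less decline at 1-month and 3-month follow-up than usual rehabilitation therapy", with no exception for any measure.

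The data collection is narrower:

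- In the Schedule of Evaluations, AMPS is marked at baseline, post-intervention and 1 month, and AM-PAC at all four times. The row "OASIS self-care items from chart review" is marked at baseline and post-intervention only.
- The text on the baseline and post-intervention evaluations confirms that the coordinator extracts the "OASIS self-care item scores (scores at the start of care and discharge) from medical chart", and nothing later.
- The list introduced by "The following assessments will be administered during the one-month follow-up evaluation visit" includes AMPS and AM-PAC but not OASIS.
- The 3-month evaluation is by telephone. The list introduced by "The following assessments will be administered during the final evaluation" has two entries: AM-PAC and the adverse events questionnaire.

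The Data analysis section begins "Since ADL and physical functioning outcomes will be collected over three time points (baseline, post-treatment, one-month follow-up" and then specifies a mixed-effects linear regression with a quadratic growth curve. Aim 1 applies such a model separately to each of the three ADL measures.

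**The concern.** The hypothesis promises follow-up results that the trial will not have. For the primary outcome, nothing is measured at 3 months, so a 3-month claim about it cannot be assessed. For OASIS, a smaller decline after discharge cannot be assessed at either follow-up.

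The 3-month part of the primary objective therefore rests on AM-PAC alone, a patient-reported measure taken by telephone. The analysis plan's description of the data leaves that visit out. Whether the 3-month value enters the model, how time is coded and which contrast is reported would have to be settled later, possibly with the data in view. A report could also imply a lasting 3-month effect on ADL in general when one secondary measure supplies all the evidence.

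This does not look like deliberate shorthand. The four physical-function tests have the same visit schedule as AMPS, and their hypothesis correctly stops at "less decline at one-month follow-up than usual rehabilitation therapy".

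**Working it through.** The documents give no power, alpha or sample-size figure on this point, so there is no stated number to reproduce. The check is a count, a check of whether the planned model can be estimated, and one illustration.

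**1. Claimed visits against scheduled visits.** Inputs are the primary hypothesis, the Schedule of Evaluations and the visit lists. The OASIS discharge score is counted as treatment completion.

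| Measure | Completion | 1 month | 3 months | Values per patient, with baseline |
|---|---|---|---|---|
| AMPS Motor (primary) | yes | yes | **none** | 3 |
| OASIS self-care | yes | **none** | **none** | 2 |
| AM-PAC | yes | yes | yes | 4 |

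- Comparisons implied: 3 measures × 3 visits = 9. With data: 2 + 1 + 3 = 6. Without data: 9 − 6 = 3.
- Follow-up comparisons (the decline part of the hypothesis): 3 × 2 = 6, of which 3 have no data.
- At 3 months, 2 of 3 measures have no data, including the primary outcome.

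**2. Scheduled visits against the analysis plan.** The plan names baseline, post-treatment and 1 month. Of the 6 comparisons with data, 5 fall within those times. The sixth, AM-PAC at 3 months, does not. Three time points is the right number for 1 of the 3 ADL measures.

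**3. Quadratic trend for OASIS.** Take a model with columns 1, t, t², g, g·t and g·t², where g is group. Each group contributes rank min(number of distinct times, 3), so with visits common to all patients:

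- AMPS: 2 × 3 = 6 of 6
- AM-PAC: 2 × min(4, 3) = 6 of 6
- OASIS: 2 × 2 = 4 of 6

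The OASIS quadratic is then not estimable. If time is coded in days and discharge dates differ, full rank is possible. The curvature then comes only from differences between patients in discharge date, not from change within a patient.

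**4. Why time coding matters once AM-PAC has four visits (illustration only).** Assume true group differences d = (0, 1, 1, 1) at baseline, completion, 1 month and 3 months. Baseline is day 0, and follow-ups are 30 and 90 days after completion. For four points, the residual from a least-squares quadratic is r = w(w·d)/(w·w), with wᵢ = 1/∏(tᵢ − tⱼ) over j ≠ i.

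- Completion at day 42 (t = 0, 42, 72, 132): w × 10⁶ = (−2.505, 8.818, −7.716, 1.403), w·d = 2.505, w·w = 145.54, ratio 0.0172. Fitted differences after baseline: 1 − 0.152 = 0.85, 1 + 0.133 = 1.13, 1 − 0.024 = 0.98.
- Completion at day 90 (t = 0, 90, 120, 180): w × 10⁶ = (−0.514, 4.115, −4.630, 1.029), w·d = 0.514, w·w = 39.69, ratio 0.0130. Fitted differences: 1 − 0.053 = 0.95, 1 + 0.060 = 1.06, 1 − 0.013 = 0.99.

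A group-by-visit term returns 1, 1, 1. Both completion days are assumptions.

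**The case against.** The strongest reply has four parts.

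- **No contrast is stated for any outcome at any visit**, so singling out AM-PAC is selective. This is true, and nothing here should be read as saying that the AMPS contrast is specified. But only for AM-PAC at 3 months is the time point missing as well.
- **The natural reading is to fit the AM-PAC model to all scheduled values**, since the model family and the quadratic form are given. An analyst could do that. The text nevertheless names three times, and following it literally drops the only 3-month ADL data.
- **The three-time-point sentence covers physical function too**, and it is right for AMPS plus the four physical tests, 5 of the 7 modelled outcomes. That is correct. The sentence is still wrong for two of the three ADL measures, which are the ones the primary hypothesis concerns.
- **The quadratic is off by only about 1 to 2% at 3 months in the illustration**, so categorical time is partly a matter of preference. This is fair for that visit. The larger misfit, up to 15%, falls at completion, and the same AM-PAC model would supply that estimate. Naming the fourth visit and the contrast is the essential repair; categorical time is the cleaner way to do it.

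One could also say that this is a 48-patient pilot with no decision rule at 3 months, and that the objective speaks of ADL generally, for which AM-PAC does give 3-month data. That limits the consequences. It does not change the hypothesis, which attaches every visit to every measure.

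**Conclusion.** The concern holds. The schedule and the visit lists agree with each other and contradict the hypothesis: 3 of 9 claimed comparisons have no data, including the primary outcome at 3 months. The analysis plan's time points omit the one ADL measure that reaches 3 months, and its quadratic trend is not estimable for OASIS at two common visits.

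The count rests on treating OASIS discharge as treatment completion. If discharge were not accepted as completion, the number without data would be 3 + 1 = 4 of 9. The rank result rests on visits common to all patients. The quadratic illustration rests on assumed values, and the conclusion does not depend on it.

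This should be fixed, but it does not threaten the trial: the AMPS data at completion and 1 month are intact.

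**What to change.** **Hypothesis.** Limit AMPS Motor Skills to treatment completion and 1 month, OASIS to discharge, and AM-PAC to completion, 1 month and 3 months. State that the 3-month part of the primary objective rests on AM-PAC alone.

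**Analysis plan.** Replace the general three-time-point sentence with a list of visits per outcome (AMPS 3, AM-PAC 4, OASIS 2). Fit AM-PAC on all four visits with time as a categorical visit and a group-by-visit term, and report the between-group estimate at 3 months. Analyse OASIS as a start-of-care-to-discharge comparison, for example the discharge score adjusted for the start-of-care score, with no quadratic term. Naming the contrast for AMPS in the same place would be sensible.

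**Cost.** The changes are to wording and model specification, with no new data collection. The 3-month claim becomes narrower and rests on one patient-reported telephone measure. Categorical visits use 4 time parameters per group (intercept included) against 3 for a quadratic, a small loss of precision with 48 patients.

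### The follow-up part of the ADL hypothesis is worded as less decline rather than as the effect at follow-up named in the objective, so a programme with lasting benefit can contradict it.

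*Combined protocol and SAP*

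**What the plan says.** Under Study Objectives, the Primary Objective is to estimate the preliminary effect of the programme "on improving ADL at treatment completion, one month, and 3 months after the completion". The hypothesis beneath it expects greater improvements in three ADL measures, with AMPS Motor Skills as the primary outcome, "at treatment completion and less decline at 1-month and 3-month follow-up than usual rehabilitation therapy".

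Secondary objective 1 follows the same pattern. The objective is improvement in physical functioning at completion and one month later. Hypothesis 1 expects greater improvements "at treatment completion and less decline at one-month follow-up than usual rehabilitation therapy".

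The Data analysis plan fits mixed-effects linear regressions over baseline, post-treatment and one month, in which "a quadratic growth curve is included to describe the temporal trend of the response". It names no arm-by-time contrast, neither a difference in decline nor a difference at a visit, and it gives no success rule for the ADL or physical function outcomes.

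The Schedule of Evaluations (6.1) collects AMPS and the physical function tests up to one month, AM-PAC up to three months, and OASIS self-care items at baseline and post-intervention only.

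**The concern.** The objective asks whether treated patients have improved more at one and three months. The hypothesis asks whether they lose less after treatment ends. These are different quantities. Decline from completion starts at a score measured after randomisation, one that the programme is meant to raise, so the arms are expected to start from different levels.

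What is at stake is the follow-up conclusion. If the programme produces a larger gain and part of it fades, treated patients can still be better off at one month while the hypothesis as written is contradicted. This affects AMPS Motor at one month, where the data will exist, so it is separate from the question of which measures reach three months. Because the analysis plan names neither contrast, the choice between them stays open until the data are seen.

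**Working it through.** **Inputs from the protocol.** The trial is a "pilot randomized controlled trial of 48 Medicare patients referred to HHC for skilled rehabilitation services", with 24 patients per arm. The protocol gives no SD, correlation, alpha or expected effect, so there is no figure to reproduce. The values marked as assumed below are illustrations.

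**Identity (no assumed values).** Let D(post) and D(1m) be the between-arm differences (experimental minus control) in mean change from baseline at completion and at one month. With decline measured from completion:

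control decline − experimental decline = D(1m) − D(post)

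Less decline in the experimental arm therefore requires D(1m) > D(post), which means that the advantage must grow after treatment stops.
- Advantage fully kept, D(1m) = D(post): the true contrast is 0.
- Advantage partly kept, 0 < D(1m) < D(post): the contrast is unfavourable, although the programme is still ahead.

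**Main illustration (assumed gains from baseline, SD units).** Experimental +0.6 then +0.4; control +0.2 then +0.15.
- D(post) = 0.6 − 0.2 = 0.40 and D(1m) = 0.4 − 0.15 = 0.25.
- Declines are 0.20 (experimental) and 0.05 (control). The contrast is 0.05 − 0.20 = −0.15, which equals 0.25 − 0.40.
- SE of the difference in decline = √(2(1−ρ)) × √(2/24): 0.258 for ρ = 0.6 and 0.183 for ρ = 0.8.
- P(less decline observed) = Φ(−0.15/SE): **28%** and **21%**.
- SE of the baseline-adjusted one-month difference = √(1−ρ²) × √(2/24): 0.231 and 0.173.
- P(one-month difference favours the programme) = Φ(0.25/SE): **86%** and **93%**.

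**Other assumed patterns (SD 1, no baseline adjustment, two-sided alpha 0.05, SE of the one-month difference √(2/24) = 0.289).**

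| True advantage, completion then one month | One-month difference favours programme | Power of one-month difference | Less decline observed |
|---|---|---|---|
| 0.8 then 0.8 | Φ(0.8/0.289) = 99.7% | 79.1% | 50% (significant in its favour in 2.5%) |
| 0.8 then 0.5 | Φ(0.5/0.289) = 96% | 41.0% | 14.9%, 9.0%, 1.0% (ρ = 0.5, 0.7, 0.9) |

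Parallel loss gives the same answer without any probability. With gains of +0.8 then +0.6 against +0.3 then +0.1, the programme is 0.5 ahead at both visits, and both arms decline by 0.2. The clause is not met.

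**The case against.** **Better maintenance is a legitimate, stricter prediction, and this is an estimation pilot.** That is fair. But the hypothesis puts it in place of a statement about the effect at follow-up, so the later part of the objective is left with no matching hypothesis.

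**The reference point is an inference.** This is correct. If decline were measured from baseline, the clause would equal the between-arm difference in change and the problem would vanish. Completion is the more natural reading, because the sentence sets improvement at completion against decline afterwards, and patients expected to improve are not readily described as declining from baseline. If baseline was meant, the same rewording removes the ambiguity.

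**The gains are chosen by hand and dropout is ignored.** True. The percentages show what can happen and do not measure risk in this trial. If usual-care patients go on losing function faster than treated patients, the clause would be met. The identity holds in every case.

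**Stronger readings that the documents do not support.**
- A reader might infer that a programme with no benefit could meet the hypothesis. That is possible only if the decline clause is read alone. The sentence joins it by 'and' to greater improvement at completion. If both truly hold, D(1m) = D(post) + (control decline − experimental decline) is a sum of two positive terms, so benefit at one month follows.
- A reader might infer that the pilot will be judged, or continuation decided, on the decline clause. The Data analysis plan contains no such rule.
- A reader might use the Background statement that "6% of HHC patients show no improvement in ADL status, and 36% show a decline in ADL status from admission to discharge" to argue that usual-care patients have no gain to lose. Those figures come from a cited study of home health patients between admission and discharge. They do not describe this control arm after treatment, and patients without a gain can still decline further.

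**Conclusion.** The point holds as a mismatch between objective and hypothesis that works in one direction: the stated follow-up hypothesis can be contradicted although benefit lasts. This follows from the identity once decline is read from completion, which is the one interpretive assumption. The size depends on assumed gains and correlations. In the main illustration, less decline is observed in 28% or 21% of trials, against 86% or 93% in which the baseline-adjusted one-month difference favours the programme. The mismatch affects the primary outcome at one month and the four physical function tests in Hypothesis 1. The analysis plan does not resolve it, because it names no contrast. It is worth correcting because it determines which follow-up comparison answers the objective.

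**What to change.** - Reword the primary hypothesis and Hypothesis 1 as: *greater improvement from baseline than usual rehabilitation therapy at treatment completion and at each follow-up at which the measure is collected*.
- In the Data analysis plan, state the arm-by-time terms and name the between-arm difference in change from baseline at each such visit as the contrast. For AMPS Motor and the physical function tests this means completion and one month; for AM-PAC, three months as well.
- Extend the AM-PAC model to include its three-month value, since the plan describes only three time points, ending at one month.
- Report change from completion to follow-up by arm as a supportive description of durability.
- Record the change before outcomes are compared by arm.

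The cost is the wording of two hypotheses, a named contrast and a fourth time point in one model. No new patients, visits or measurements are needed. The downside is that less decline ceases to be a formal claim. If the investigators want to keep it, it should be an additional hypothesis with its reference point stated.
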